#### **9.4.1.4 Analysis of Safety**

Descriptive statistics (mean, standard deviation, minimum, and maximum) will be produced for continuous variables, and frequency tables will be produced for discrete variables by treatment group. Summaries of adverse events and serious adverse events will be produced by treatment group. Shift tables will be generated for comparing the screening/baseline values and end of study values of the relevant measures.

For weight and height, the change from baseline to last assessment will be compared between the two treatment groups using an ANCOVA model with baseline value as a covariate and treatment as the main factor. A similar ANCOVA model will be used for the analysis of the z-scores for height. The rate of change in height will be assessed using regression analysis.

The following safety data will be summarized by treatment group:

- Adverse events (AEs), adverse drug reactions (ADRs), serious adverse events (SAEs), and serious adverse drug reactions (SADRs)
- Number of discontinuations due to AEs
- Hematology assessments
- Biochemistry assessments
- Vital signs
- Urinalysis
- Prior and concomitant medications

Prolactin will be measured at baseline and Month 12. The change in prolactin level from baseline to Month 12 will be compared between the two treatment groups using an ANCOVA model with baseline value as a covariate and treatment as the main factor.

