Patients remain in the study for 12 months or until their SF level is found to be  $\geq 1000 \mu\text{g/L}$  at 2 consecutive visits, whichever comes first. Since SF level may be impacted by the presence of infection, it must additionally be verified that the child has had no signs of infection in the previous 7 days, including the day of the visit, and that the level of C-reactive protein (CRP) is no greater than 20% higher than the normal range for the patient's age. If there are signs of infection and/or the CRP level is above this threshold, the SF level must be checked again a minimum of one week later. (Note: If an investigator has valid reason to believe that an SF level  $\geq 1000 \mu\text{g/L}$  may be attributable to infection even if this is not indicated by the CRP result, SF may be rechecked once more a minimum of one week later.)

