### **5.3 Safety Endpoints**

The safety endpoints are:

- Adverse events (AEs): Frequency, intensity, time to onset, duration, and relatedness to study drug
- Serious adverse events (SAEs): Frequency, intensity, time to onset, duration, and relatedness to study drug
- Number of discontinuations due to AEs
- Growth parameters: Weight, height, and height velocity, as classified using the Z-score system
- Change in prolactin level from baseline to Month 12

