### **5.7.8 Height and weight**

For height (cm) and weight (kg), the change from baseline to last assessment will be compared between the two treatment groups using an ANCOVA model with baseline value as a covariate and treatment as the main factor. The rate of change in height will be assessed using regression analysis.

Child growth standards for 2007 are available at the WHO website

<https://www.who.int/childgrowth/standards/en/>. This site provides mean and standard deviation for height and weight from 0 to 5 years old by day for males and females. It has mean and standard deviation for height from 5 to 19 years old by month for male and female and for weight from 5 to 10 years old by month for males and females.

Z scores will be calculated by matching sex and age in days until 5 years old and by matching sex and age in months from 5 to 10 years old as follows:

$$\text{(Observed data from LA55} - \text{Mean from WHO data}) / (\text{Standard deviation from WHO data})$$

The change from baseline to last assessment in Z score will be compared between the two treatment groups using an ANCOVA model with baseline value as a covariate and treatment as the main factor.

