### **14.3.3 Height**

Table 14.3.3.1 Height (cm) at each assessment

Table 14.3.3.2 Change in height (cm) from baseline to at each follow-up assessment

Table 14.3.3.3 LS Means for change in height (cm) from ANCOVA model at Month 12

Table 14.3.3.4 Trend analysis for height (cm) over time

Table 14.3.3.5 Z score analysis for height (cm)

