### **14.3.4 Weight**

Table 14.3.4.1 Weight (kg) at each assessment

Table 14.3.4.2 Change in weight (kg) from baseline to at each follow-up assessment

Table 14.3.4.3 LS Means for change in weight (kg) from ANCOVA model at Month 12

Table 14.3.4.4 Trend analysis for weight (kg) over time

Table 14.3.4.5 Z score analysis for weight (kg)

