Data source: 16.2.9.5 Listing of vital signs

Table 14.3.3.5 Z score analysis for height (cm)

	Deferiprone		Placebo		
	N	Mean ± SD (Min, Max)	N	Mean ± SD (Min, Max)	P-value (t-test)
Baseline	xx	x.x ± x.x (x.x, x.x)	xx	x.x ± x.x (x.x, x.x)	0.xxxx
Month 12	xx	x.x ± x.x (x.x, x.x)	xx	x.x ± x.x (x.x, x.x)	0.xxxx
Change	xx	x.x ± x.x (x.x, x.x)	xx	x.x ± x.x (x.x, x.x)	0.xxxx

Data source: 16.2.9.5 Listing of vital signs

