Data source: 16.2.9.5 Listing of vital signs

Table 14.3.4.5 Z score analysis for weight (kg)

	Deferiprone		Placebo		
	N	Mean ± SD (Min, Max)	N	Mean ± SD (Min, Max)	P-value (t-test)
Baseline	xx	x.x ± x.x (x.x, x.x)	Xx	x.x ± x.x (x.x, x.x)	0.xxxx
Month 12	xx	x.x ± x.x (x.x, x.x)	Xx	x.x ± x.x (x.x, x.x)	0.xxxx
Change	xx	x.x ± x.x (x.x, x.x)	Xx	x.x ± x.x (x.x, x.x)	0.xxxx

Data source: 16.2.9.5 Listing of vital signs

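### SAP 5.7.8 plans a baseline-adjusted ANCOVA of growth Z-score change to last assessment, but the only Z-score tables show an unadjusted t-test at Month 12

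*SAP*

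**What the plan says.** The SAP's safety endpoints (5.3) include "Growth parameters: Weight, height, and height velocity, as classified using the Z-score system". For the analysis, SAP 5.7.8 says: "The change from baseline to last assessment in Z score will be compared between the two treatment groups using an ANCOVA model", with the baseline value as covariate and treatment as factor. It plans the same model, also to last assessment, for height in cm and weight in kg. Protocol 9.4.1.4 agrees on the method for height: "A similar ANCOVA model will be used for the analysis of the z-scores for height".

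The outputs differ from this text.

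- Tables 14.3.3.5 and 14.3.4.5 are the only Z-score tables. Their shells have rows for baseline, Month 12 and change, and a t-test P value. They have no LS mean, covariate, confidence interval or last-assessment row.
- The only growth ANCOVA tables are in raw units and tied to Month 12: "Table 14.3.3.3 LS Means for change in height (cm) from ANCOVA model at Month 12" and "Table 14.3.4.3 LS Means for change in weight (kg) from ANCOVA model at Month 12".
- Tables 14.3.3.1, 14.3.3.2, 14.3.4.1 and 14.3.4.2 give height and weight, and their changes, month by month. Tables 14.3.3.4 and 14.3.4.4 give slopes. None of these is limited to children who reach Month 12.

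Follow-up depends on response. SAP 3.1 says: "Patients remain in the study for 12 months or until their SF level is found to be" at or above 1000 µg/L at two consecutive visits, whichever comes first. Protocol 5.1 has weight and height measured at the early termination visit.

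**The concern.** The text and the tables describe two different analyses, and they may use different children. The text takes every child with a post-baseline measurement and adjusts for baseline Z. The shells, read literally, take only children measured at Month 12 and do not adjust.

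A child whose ferritin rises past the threshold leaves early, and the plan expects this far more often on placebo. A literal Month 12 comparison would therefore set most of the deferiprone arm against placebo children selected for slow ferritin rise. That is no longer the randomised comparison, and it is less precise.

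Growth matters in this trial. Protocol 1.1 gives growth delay in young children with mild iron overload, seen with deferoxamine, as the reason for deferring chelation. The analysis in the text is feasible, because growth is measured monthly and at early termination.

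**Working it through.** **Inputs.** There are 32 children per arm (SAP 3.2). The expected proportions with ferritin below 1000 µg/L at Month 12 are 70% and 20% (Protocol 9.2). Alpha is 0.05 two-sided (SAP 5). The documents give no power, standard deviation or effect size for growth, so growth results below are in SD units.

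**The plan's own figure.** Protocol 9.2 claims over 90% power for the primary endpoint. With the pooled z formula, (0.5 × √32 − 1.96 × √(2 × 0.45 × 0.55)) / √(0.21 + 0.16) = 2.38, so power is 99.1%. Exact enumeration of Fisher's test gives 98.3%. The claim reproduces.

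**Children at Month 12, taking the endpoint rate as attendance.** 0.70 × 32 = 22.4 and 0.20 × 32 = 6.4.

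**Precision.** The standard error of a difference in means is √(1/n1 + 1/n2). The difference detectable at 80% power is (1.960 + 0.842) × SE, before any gain from a covariate.

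| Children (deferiprone v placebo) | SE (SD units) | Ratio to 32 v 32 | Detectable difference |
|---|---|---|---|
| 32 v 32, last assessment | 0.250 | 1.0 | 0.70 SD |
| 22.4 v 6.4, planning rates | 0.448 | 1.79 | 1.26 SD |
| 25 v 12, assumed | 0.351 | 1.40 | 0.98 SD |
| 22.4 v 16, assumed | 0.327 | 1.31 | 0.92 SD |

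Rounding to 22 v 6 gives an SE of 0.461 and a ratio of 1.84. The two assumed rows allow for children who attend Month 12 with ferritin already at or above 1000.

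**Selection, as an illustration.** Suppose there is no growth effect. Keep the 70% and 20% of children with the slowest ferritin rise, and let rho be the correlation between ferritin rise and growth change. The documents do not give rho. The mean of a standard normal below its p-quantile is −φ(z_p)/p, which is −0.497 for p = 0.70 and −1.400 for p = 0.20. The spurious difference (deferiprone minus placebo) is rho × 0.903, that is ±0.09, ±0.27 and ±0.45 SD for rho = ±0.1, ±0.3 and ±0.5. The sign is unknown.

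**Loss from not adjusting.** With equal variances and correlation r between baseline and follow-up Z, the variance under ANCOVA relative to the change score is (1 − r²)/(2(1 − r)) = (1 + r)/2. This is 0.75 for r = 0.5 and 0.975 for r = 0.95 (r assumed). The missing adjustment costs less than the possible restriction to Month 12.

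**The case against.** A reader might infer that the growth safety result will come from children selected by response. The documents do not establish that. Section 5.7.8 is the methods text and is clear. The introduction to the shells allows the final layout to differ, and a note allows more tables. What is shown is an unresolved conflict. The same documents do not settle it, however. The SAP's introduction presents the shells as the tables for the study report, and its precedence rule covers SAP against protocol, not SAP text against SAP shells. Month 12 is also in the titles of the raw ANCOVA tables. Elsewhere the SAP draws LS-mean shells where it means ANCOVA, and labels rows as last assessment in the shift tables.

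The second argument is that Month 12 may include early leavers. The last column of the visit schedule covers Month 12 or end of study, SAP 4.2.2 assigns end-of-study procedures to the early termination visit, and growth is measured there. On that reading most of the selection problem goes. The shells do not say so, and the baseline-adjusted Z-score analysis is missing either way.

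Two further inferences also go too far. One is that 22 v 6 is the expected attendance. Exit needs two consecutive values, checked for infection, so children who first cross at Month 11 or 12 still attend. Dropout for other reasons works the other way. The other is that the remaining growth data are discarded. The monthly and slope tables use them, and the raw LS-means tables keep the baseline adjustment.

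The last objection also stands. Moving the raw cm and kg analyses to last assessment is not a clean remedy. In the earlier investigator-led trial described in Protocol 1.3, all unchelated children reached the threshold at about 6 months. Placebo children who leave sooner have less time to grow, so raw change would favour deferiprone and could hide a growth delay.

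**Conclusion.** The point holds as a conflict between text and tables. The SAP plans a baseline-adjusted Z-score ANCOVA to last assessment, and no listed output delivers it for an endpoint that the SAP itself defines by Z-score. This part needs no assumption.

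The consequence is conditional. It requires that the shells are produced as drawn and that Month 12 excludes early-termination visits. The Z-score comparison is then response-selected, with a standard error about 1.8 times that of 32 v 32 at the planning rates, or about 1.3 to 1.4 times under the assumed higher placebo attendance. The direction and size of any selection bias cannot be derived from the documents. Growth is one of several safety endpoints and has no stated power, and the monthly and slope tables are unaffected. The correction is still worth making before unblinding, because it fixes which growth analysis is reported.

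**What to change.** Redraw Tables 14.3.3.5 and 14.3.4.5 with rows for baseline, last assessment and change. Replace the t-test with the ANCOVA LS-mean difference and 95% confidence interval, adjusted for baseline Z. State whether Month 12 in any growth table includes early-termination visits. Keep Month 12 Z-scores as description with N per arm, and report time on study by arm.

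For Tables 14.3.3.3 and 14.3.4.3, reconcile the Month 12 titles with the last-assessment wording of 5.7.8. Do not rely on change in cm or kg to last assessment without accounting for follow-up time. Rest the growth conclusion on the age-standardised Z-score and the slope analyses.

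The cost is small shell and programming edits, with no new data. Some inequality in follow-up between arms remains. Age standardisation reduces its effect but does not remove it.

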### **Impact of COVID-19 on the primary efficacy endpoints**

Sensitivity analyses may be performed, if warranted, by excluding data that might have been impacted by COVID-19.

## **SUMMARY TABLES AND FIGURES**

Summary tables and figures are numbered following ICH structure.

**Note: The final numberings for tables and/or figures in the clinical study report can be changed if more tables and/or figures are made in the addition to those in the SAP.**

### **TABLES**

#### **14.1 Patient disposition, demographics, and baseline data**

Table 14.1.1 Patient disposition

Table 14.1.2 Number of patients by study site

Table 14.1.3 Number of patients in safety, ITT, and PP populations

Table 14.1.4 Reasons for not completing the study

Table 14.1.5 Demographics data

Table 14.1.6 Medical history

Table 14.1.7 Serum ferritin, LPI, and TSAT at baseline

#### **14.2 Efficacy analyses**

##### **14.2.1 Serum ferritin ( $\mu\text{g}/\text{L}$ )**

Table 14.2.1.1 Serum ferritin ( $\mu\text{g}/\text{L}$ ) at each assessment – ITT population

Table 14.2.1.1a Serum ferritin ( $\mu\text{g}/\text{L}$ ) at each assessment – PP population

Table 14.2.1.2 Change in serum ferritin ( $\mu\text{g}/\text{L}$ ) from baseline at each follow-up assessment – ITT population

Table 14.2.1.2a Change in serum ferritin ( $\mu\text{g}/\text{L}$ ) from baseline at each follow-up assessment – PP population

Table 14.2.1.3 LS Means for change in serum ferritin ( $\mu\text{g}/\text{L}$ ) from ANCOVA model at each follow-up assessment – ITT population

Table 14.2.1.3a LS Means for change in serum ferritin ( $\mu\text{g}/\text{L}$ ) from ANCOVA model at each follow-up assessment – PP population

Table 14.2.1.4 Trend analysis for serum ferritin ( $\mu\text{g}/\text{L}$ ) over time – ITT population

Table 14.2.1.4a Trend analysis for serum ferritin ( $\mu\text{g}/\text{L}$ ) over time – PP population

Table 14.2.1.5 Percent of patients who had serum ferritin  $< 1000 \mu\text{g}/\text{L}$  at each assessment – ITT population

Table 14.2.1.5a Percent of patients who had serum ferritin  $< 1000 \mu\text{g}/\text{L}$  at each assessment – PP population

##### **14.2.2 Labile plasma iron ( $\mu\text{M}$ )**

Table 14.2.2.1 LPI ( $\mu\text{M}$ ) at each assessment – ITT population

Table 14.2.2.1a LPI ( $\mu\text{M}$ ) at each assessment – PP population

Table 14.2.2.2 Change in LPI ( $\mu\text{M}$ ) from baseline at each follow-up assessment – ITT population

Table 14.2.2.2a Change in LPI ( $\mu\text{M}$ ) from baseline at each follow-up assessment – PP population

Table 14.2.2.3 LS Means for change in LPI ( $\mu\text{M}$ ) from ANCOVA model at each follow-up assessment – ITT population

Table 14.2.2.3a LS Means for change in LPI ( $\mu\text{M}$ ) from ANCOVA model at each follow-up assessment – PP population

Table 14.2.2.4 Trend analysis for LPI ( $\mu\text{M}$ ) over time – ITT population

Table 14.2.2.4a Trend analysis for LPI ( $\mu\text{M}$ ) over time – PP population

Table 14.2.2.5 Percent of patients who had LPI  $< 0.6 \mu\text{M}$  at each assessment – ITT population

Table 14.2.2.5a Percent of patients who had LPI  $< 0.6 \mu\text{M}$  at each assessment – PP population

### **14.2.3 Transferrin saturation (%)**

Table 14.2.3.1 TSAT (%) at each assessment – ITT population

Table 14.2.3.1a TSAT (%) at each assessment – PP population

Table 14.2.3.2 Change in TSAT (%) from baseline at each follow-up assessment – ITT population

Table 14.2.3.2a Change in TSAT (%) from baseline at each follow-up assessment – PP population

Table 14.2.3.3 LS Means for change in TSAT (%) from ANCOVA model at each follow-up assessment – ITT population

Table 14.2.3.3a LS Means for change in TSAT (%) from ANCOVA model at each follow-up assessment – PP population

Table 14.2.3.4 Trend analysis for TSAT (%) over time – ITT population

Table 14.2.3.4a Trend analysis for TSAT (%) over time – PP population

Table 14.2.3.5 Percent of patients who had TSAT  $< 60\%$  at each assessment – ITT population

Table 14.2.3.5a Percent of patients who had TSAT  $< 60\%$  at each assessment – PP population

## **14.3 Safety analyses**

### **14.3.1 Adverse events**

Table 14.3.1.1 Overall summary of adverse events

Table 14.3.1.2 Adverse events

Table 14.3.1.3 Most common Adverse Events  $\geq 5$  percent

Table 14.3.1.4 Adverse events with the maximum severity/intensity

Table 14.3.1.5 Adverse drug reactions

Table 14.3.1.6 Most common Adverse drug reactions  $\geq 5$  percent

Table 14.3.1.7 Adverse drug reaction with the maximum severity/intensity

Table 14.3.1.8 Serious adverse events

Table 14.3.1.9 Serious adverse events with the maximum severity/intensity

Table 14.3.1.10 Serious adverse drug reactions

Table 14.3.1.11 Serious adverse drug reactions with the maximum severity/intensity

Table 14.3.1.12 Adverse events by relatedness to study medication

Table 14.3.1.13 Adverse events – event count and rate

### **14.3.2 Vital signs**

Table 14.3.2.1 Temperature (C) Heart rate at each assessment

Table 14.3.2.2 Change in temperature (C) from baseline at each follow-up assessment

Table 14.3.2.3 Heart rate (bpm) at each assessment

Table 14.3.2.4 Change in heart rate (bpm) from baseline to each follow-up assessment

Table 14.3.2.5 Diastolic blood pressure (mmHg) at each assessment

Table 14.3.2.6 Change in diastolic blood pressure (mmHg) from baseline at each follow-up assessment

Table 14.3.2.7 Systolic blood pressure (mmHg) at each assessment

Table 14.3.2.8 Change in systolic blood pressure (mmHg) from baseline at each follow-up assessment

### **14.3.3 Height**

Table 14.3.3.1 Height (cm) at each assessment

Table 14.3.3.2 Change in height (cm) from baseline to at each follow-up assessment

Table 14.3.3.3 LS Means for change in height (cm) from ANCOVA model at Month 12

Table 14.3.3.4 Trend analysis for height (cm) over time

Table 14.3.3.5 Z score analysis for height (cm)

### **14.3.4 Weight**

Table 14.3.4.1 Weight (kg) at each assessment

Table 14.3.4.2 Change in weight (kg) from baseline to at each follow-up assessment

Table 14.3.4.3 LS Means for change in weight (kg) from ANCOVA model at Month 12

Table 14.3.4.4 Trend analysis for weight (kg) over time

Table 14.3.4.5 Z score analysis for weight (kg)

### **14.3.5 Concomitant medications**

Table 14.3.4.1 Concomitant medications

### **14.3.6 Laboratory data**

#### **14.3.6.1 Hematology**

Table 14.3.6.1.1 Hematology data at each assessment

Table 14.3.6.1.2 Change in hematology data from baseline to each follow-up assessment

Table 14.3.6.1.3 Shift table for hematology data: deferiprone group

Table 14.3.6.1.4 Shift table for hematology data: placebo group

#### **14.3.6.2 Biochemistry**

Table 14.3.6.2.1 Biochemistry data at each assessment

Table 14.3.6.2.2 Change in biochemistry data from baseline to at each follow-up assessment

Table 14.3.6.2.3 Shift table for biochemistry data: deferiprone group

Table 14.3.6.2.4 Shift table for biochemistry data: placebo group

Table 14.3.6.2.5 Percent of patients who had ALT > 2 x ULN, 3 x ULN, or 5 x ULN during the study

Table 14.3.6.2.6 Percent of patients who had AST > 2 x ULN, 3 x ULN, or 5 x ULN during the study

### **14.3.7 Prolactin**

Table 14.3.7.1 Prolactin at each assessment

Table 14.3.7.2 Change in prolactin from pre-dose to Month 12

Table 14.3.7.3 LS Means of change in prolactin from pre-dose to Month 12 from the ANCOVA model

### **14.4 Other analyses**

Table 14.4.1 Compliance (%) at each assessment

Table 14.4.2 Overall mean of transfusional iron input (mg/kg/day) during the study

Table 14.4.3 Overall mean of total daily dose (mg/kg/day) during the study

Table 14.4.4 Patient exposure to study medication

Table 14.4.5 Duration of study drug exposure

## **FIGURES**

### **14.2 Efficacy**

Figure 14.2.1 Mean line graph for serum ferritin over time

Figure 14.2.2 Mean line graph for LPI over time

Figure 14.2.3 Mean line graph for TSAT over time

Figure 14.2.4 Mean line graph for change from baseline in serum ferritin over time

Figure 14.2.5 Mean line graph for change from baseline in LPI over time

Figure 14.2.6 Mean line graph for change from baseline in TSAT over time

Figure 14.2.7 Kaplan-Meier survival curve for the time to reach serum ferritin level  $\geq 1000 \mu\text{g/L}$

Figure 14.2.8 Kaplan-Meier survival curve for the time to reach LPI value  $\geq 0.6 \mu\text{M}$

Figure 14.2.9 Kaplan-Meier survival curve for the time to reach TSAT value  $\geq 60\%$

### **14.3 Safety**

#### **14.3.1 Hematology**

Figure 14.3.1.1 Mean line graph for the hematology data over visit

Figure 14.3.1.2 Proportion of patients with abnormal hematology data at each assessment

Figure 14.3.1.3 ANC graphs for patients with neutropenia

Figure 14.3.1.4 ANC graphs for patients with agranulocytosis

#### **14.3.2 Biochemistry**

Figure 14.3.2.1 Mean line graph for the biochemistry data over visit

Figure 14.3.2.2 Proportion of patients with abnormal biochemistry data at each assessment

### **16.1.9 Documents of Statistical Methods**

SAS output 16.1.9.1 Kaplan-Meier survival analysis for the time to reach serum ferritin level  $\geq 1000 \mu\text{g/L}$

SAS output 16.1.9.2 Kaplan-Meier survival analysis for the time to reach LPI value  $\geq 0.6 \mu\text{M}$

SAS output 16.1.9.3 Kaplan-Meier survival analysis for the time to reach TSAT value  $\geq 60\%$

SAS output 16.1.9.4 Kaplan-Meier survival analysis for the time to be withdrawn from the study

## DATA LISTINGS

Data listings are numbered following ICH structure.

**Note: The final numberings for Patient data listings in the clinical study report can be changed if more Patient data listings are made in the addition to those in the SAP.**

### **16.2.1 Discontinued patients**

- 16.2.1.1 Listing of disposition
- 16.2.1.2 Listing of withdrawals due to AEs

